9.11.4 Incomplete End Date of Study Treatment Date

- In case the last date of study drug is missing or incomplete the date of last administration of study drug will be taken from the treatment termination eCRF pages.
- If the last date of study drug is completely missing and there is no End of Treatment eCRF
 page and no death date, study treatment should be considered to be ongoing and the cut-off
 date should be used in the analysis as the last dosing date.
- If the last date of study drug is completely or partially missing and there is either an End of Treatment eCRF page OR a death date available (within the cut-off date) then imputed last dose date is:
 - = 31DECYYYY, if only Year is available and Year < Year of min (EOT date, death date)
 - = Last day of the month, if both Year and Month are available and Year = Year of min (EOT date, death date) and Month < the month of min (EOT date, death date)
 - = min (EOT date, death date), for all other cases

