SAE Serious Adverse Event SAF Safety Analysis Set

SD Stable Disease or Standard Deviation

SDTM Study Data Tabulation Model

SOC System Organ Class

TEAE Treatment-Emergent Adverse Event

WHO-DD World Health Organization Drug Dictionary

3 Modification History

Unique Identifier for Version	Date of IAP Version	Author	Changes from the Previous Version
1.0	14Apr2021	PPD	N/A: First version

4 Purpose of the Integrated Analysis Plan

The purpose of this IAP is to document technical and detailed specifications for the analysis of data collected for protocol MS201922-0001 - Part C.

The study was prematurely terminated by the sponsor and an abbreviated study report will be written.

Results after the database lock for the final analysis will be included in the abbreviated Clinical Study Report (aCSR). Additionally, the planned analyses identified in this IAP may be included in regulatory submissions or future manuscripts. Any post-hoc, or unplanned analyses performed to provide results for inclusion in the aCSR but not identified in this prospective IAP will be clearly identified in the aCSR.

The IAP is based on Section 8 (Statistics) of the study protocol and protocol amendments and is prepared in compliance with ICH E9. It describes analyses planned in the protocol and protocol amendments.

5 Objectives and Endpoints

Objectives	Endpoints (Outcome Measures)	IAP section
Primary		
To evaluate the efficacy of M4344 in terms of confirmed objective response.	Objective response according to Response Evaluation Criteria in Solid Tumors version 1.1 (RECIST v1.1) as assessed by Investigator	Section 14.1
To evaluate the safety and tolerability of M4344	Occurrence of: treatment-emergent adverse events (TEAEs) and treatment-related TEAEs, as per NCI-CTCAE v5.0 Laboratory abnormalities Clinically significant abnormal vital signs Clinically significant abnormal ECGs	Section 15
Secondary		
To evaluate the duration of response for subjects receiving M4344	Duration of response according to RECIST v1.1, as assessed by Investigator	Section 13
To evaluate the overall survival (OS) for subjects receiving M4344	os	Section 14.3
To evaluate the progression-free survival (PFS) for subjects receiving M4344	PFS according to RECIST v1.1 as assessed by Investigator	Section 14.4
To evaluate the PK of M4344	No PK parameter estimates of M4344 will be provided.	Section 16.1

6 Overview of Planned Analyses

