Study Part C was to explore potential antitumor efficacy and aimed to confirm the safety and tolerability of single agent M4344. Parts C1-C3 planned to enroll participants whose tumors harbored loss-of-function mutations in one or more of the following genes ARID1A (C1), ATRX and/or DAXX (C2), ATM (C3).

The study Part C was stopped after 13 subjects were enrolled; and therefore, only a final analysis will be conducted. Due to the low number of cohorts and participants, it was decided to reduce the scope of the TLFs. Data will not be summarized per Part. Where appropriate, only listings will be provided. Details are provided in the respective sections.

Statistical analyses will be performed using CDISC SDTM data. These SDTM data contain as clean as possible eCRF data, as well as external data, including laboratory data, biomarker data, and electrocardiogram data. A data review meeting will be held prior to the database lock. In addition, no database can be locked until this IAP has been approved.

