6.1 Interim Analyses

No interim analysis will be performed as this study was stopped prematurely.

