6.2 Final Analysis

All final, planned analyses identified for Part C in the Clinical Trial Protocol and in this IAP will be performed after the last participant last visit for Part C.

7 Changes to the Planned Analyses in the Clinical Study Protocol

Only analyses of Part C of the trial are covered in this IAP. Analyses on other parts of the trial are described in separate documents.

Due to the premature discontinuation of study Part C and the low number of subjects enrolled, the scope of the statistical analysis is reduced. The table in Section 5 indicates which objectives were not addressed.

8 Analysis Populations and Subgroups

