Planned cumulative dose (mg) = Cohort dose (mg/administration) × duration of exposure (days)

Dose intensity

Relative dose intensity

The relative dose intensity (%) is calculated by dividing the dose intensity by the planned daily dose of the study drug.

The following will be summarized:

- Duration of therapy (weeks): by summary statistics and counts/percentages of the following categories: ≤ 3 weeks, > 3 - 6 weeks, > 6 - 9 weeks, > 9 - 12 weeks, > 12 weeks
- Total number of administrations
- Total cumulative doses (mg)
- Dose intensity (mg/day)
- Relative dose intensity (%): by summary statistics and counts/percentages of the following categories: < 60%, ≥ 60% - < 80%, ≥ 80% - < 90%, ≥ 90% - ≤110%, >110%
- Minimum dose compliance (%): < 50%; ≥ 50% < 70%; ≥ 70% < 90%; ≥ 90% relative to initially planned dose

14 Efficacy Analyses

Analysis Set: FAS/SAF

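### Part C IAP 9.11.4 sets a missing last-dose date to the cut-off as if treatment were ongoing, although Part C was terminated and is analysed once, after the last visit (minor)

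*SAP*

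**What the plan says.** Section 9.11.4 of the Part C IAP has three steps.

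- First step: for a missing or incomplete last-dose date, the date of last administration of "study drug will be taken from the treatment termination eCRF pages".
- Second step, at issue here: it applies when the last-dose date is completely missing and neither an End of Treatment form nor a death is on record. Its wording includes "page and no death date, study treatment should be considered to be ongoing and the cut-off". The imputed value is then fixed by the instruction that this "date should be used in the analysis as the last dosing date".
- Third step: it handles missing or partial dates when an End of Treatment page or a death date exists.

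The same IAP describes the setting.

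- Section 4: "The study was prematurely terminated by the sponsor and an abbreviated study report will be written".
- Section 6: "The study Part C was stopped after 13 subjects were enrolled; and therefore, only a final analysis will be conducted".
- Section 6.1: "No interim analysis will be performed as this study was stopped prematurely".
- Section 6.2: the final Part C analyses "will be performed after the last participant last visit for Part C".

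The last-dose date feeds duration of exposure, planned cumulative dose, dose intensity and relative dose intensity (section 13). It also sets the on-treatment period (section 9.10), which defines treatment-emergent adverse events (section 15.1) and the worst on-treatment laboratory grades (section 15.3).

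**The concern.** An ongoing-treatment rule suits a data cut taken while people are still on drug. There, a missing end date usually means that dosing continues, and the cut-off is a sensible bound. Part C has no such cut. Once the last participant's last visit has passed in a terminated study, a treated participant with no last-dose date, no End of Treatment page and no death date is someone whose stopping was not documented. The cut-off is then the latest date the analysis could assign, and nothing in the IAP supports it as a date of dosing.

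What is at stake is one participant's exposure figures and, for longer gaps, which adverse events and laboratory values count as on-treatment. With 13 participants, one record is 1/13 = 7.7% of every denominator. The adverse event and laboratory summaries serve a primary objective in section 5. Exposure is not a listed objective.

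**Working it through.** The plan states no exposure figure to reproduce, so the check applies its own formulas to an assumed case.

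**Inputs from the Part C IAP**
- Duration of exposure in weeks = (last dose − first dose + 1)/7 (section 13).
- Planned cumulative dose = cohort dose × duration in days (section 13). The analysis group is 250 mg once daily (section 9.1).
- The on-treatment period ends at the earliest of last dose + 30 days, the cut-off and death (section 9.10).
- 13 participants (section 6).

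**Assumptions**
- T = true days from first to last dose, inclusive. The main example uses 42.
- G = days from the true last dose to the cut-off, varied from 7 to 180. The IAP gives no cut-off date.
- Every daily dose is taken during T.
- The dose intensity formula is not readable in the copy used here. From its unit (mg/day) it is taken as cumulative dose divided by days.

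**Effect of setting the last dose to the cut-off**
- Duration becomes (T + G)/7, an excess of G/7 weeks.
- Planned dose becomes 250 × (T + G) mg, an excess of 250 × G mg.
- On-treatment window: the true end is day T + 30, or T + G if sooner. The imputed end is T + G. The excess is G − 30 days if G exceeds 30, otherwise none.
- Relative dose intensity becomes T/(T + G), but only if cumulative dose stays at what was recorded.

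**Results for T = 42 (true duration 42/7 = 6.0 weeks)**

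| G (days) | Duration (weeks) | Window excess (days) | Relative dose intensity, if cumulative dose is not extended |
|---|---|---|---|
| 7 | 49/7 = 7.0 | 0 | 42/49 = 85.7% |
| 30 | 72/7 = 10.3 | 0 | 42/72 = 58.3% |
| 60 | 102/7 = 14.6 | 30 | 42/102 = 41.2% |
| 90 | 132/7 = 18.9 | 60 | 42/132 = 31.8% |
| 180 | 222/7 = 31.7 | 150 | 42/222 = 18.9% |

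At G = 90, planned dose is 250 × 132 = 33,000 mg instead of 250 × 42 = 10,500 mg. The participant moves from the category of more than 3 to 6 weeks into the category above 12 weeks. Mean duration over 13 participants shifts by (90/7)/13 = 0.99 weeks. At G = 30 the shift is 0.33 weeks, and at G = 180 it is 1.98 weeks.

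**The case against.** The strongest reply is that this is leftover template wording that will probably never be used. All three items must be absent, and the treatment termination pages are consulted first. Section 6 provides for data that are as clean as possible and for a data review meeting before lock. Section 10.1 tabulates treatment discontinuation by reason. Among 13 people, a treated participant lacking all three items would be an obvious query. This stands, and it is why the point is minor. It does not make the rule right, because an imputation rule exists for the record that survives cleaning.

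A reader might also infer three stronger things that the document does not support.

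- *That the plan invents months of exposure.* There is no cut-off date and no known affected participant, so the excess could be nil, days or months. If a participant's doses are individually dated through the last one, the last-dose date is not missing and the rule does not fire.
- *That relative dose intensity collapses.* The last column of the table rests on a reconstructed formula and on cumulative dose not being extended. Section 9.9 refers to drug start and end dates, so dosing may be held as intervals. Closing an open interval at the cut-off might extend the cumulative dose as well, and the ratio would then not fall.
- *That every later adverse event becomes on-treatment.* Events within 30 days of the true last dose count anyway, gaps of 30 days or less add nothing, and someone lost to follow-up has few later records.

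Finally, the IAP never says outright that nobody is on drug at the cut-off, and Table 3 keeps a censoring category for participants ongoing in the study. That category concerns study follow-up for PFS. Nothing in the IAP describes dosing beyond the last visit, so the inference is reasonable, but it remains an inference.

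**Conclusion.** Wrong as written, and minor. The branch presumes ongoing treatment in an analysis whose timing gives no ground for it, so any value it produces is unsupported. If such a record remains at lock, duration of exposure and planned dose can be overstated by up to the gap between the true last dose and the cut-off. The on-treatment window is lengthened only when that gap exceeds 30 days. Relative dose intensity falls only if cumulative dose is not extended too. The actual size cannot be stated. The 18.9 against 6.0 weeks assumes 42 true days and a 90-day gap, neither of which is in the IAP.

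**What to change.** Delete the ongoing-treatment branch of section 9.11.4 for this final analysis. For a completely missing last-dose date with no End of Treatment page and no death date:

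1. Use the latest M4344 dosing date recorded on the M4344 Administration Details page, which section 13 already makes the source for all dosing calculations.
2. If there is none, use the earlier of the study discontinuation date and the date of last contact. Section 9.9 bounds last contact by the cut-off, so this fallback cannot exceed the value the present rule assigns.

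The text should say whether the start of an open-ended dosing record counts as a recorded dosing date. Section 9.11 already requires imputed values to be flagged in listings, so nothing need be added there.

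The cost is one bullet of text and a few lines of programming. The downside is that exposure for that participant may be somewhat understated (step 1) or overstated (step 2).

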9.11.5 Incomplete Death Date

For the purpose of survival analyses partially missing death dates will be imputed as follows:

If only the day is missing, the death date will be imputed to the maximum of the day after the date of last contact and the 15th day of the month.

Otherwise it will not be imputed.

Imputation of Death Date is used for survival analyses only. In the death listings, non-imputed data will be presented.

9.11.6 Incomplete Tumor Assessment Dates

All investigation dates (e.g. X-ray, CT scan) must be completed with day, month and year.

If there are multiple scan dates associated with an evaluation, i.e., radiological assessments occur over a series of days rather than the same day, the choice of date of assessment could impact the date of progression and/or date of response. If there are multiple scan dates associated with an evaluation, the earliest of the scan dates associated with the evaluation will be used as the date of assessment.

If one or more investigation dates for an evaluation are incomplete but other investigation dates are available, the incomplete date(s) are not considered for calculation of the assessment date and assessment date is calculated as the earliest of the complete investigation dates (e.g. X-ray, CT-scan).

If all measurement dates for an evaluation have no day recorded, the 1st of the month is used.

If the month is not completed, for any of the investigations for an evaluation, the respective assessment will be imputed as the date which is exactly between the previous and the following assessment. If both a previous and following assessments are not available, this assessment will not be used for any calculations.

9.11.7 Incomplete Subsequent Anti-Cancer Therapy Dates

Incomplete dates for start date of subsequent anti-cancer therapy (drug therapy, radiation, surgery) will be imputed as follows and will be used for determining censoring dates for some efficacy analyses.

- If only day is missing, it will be imputed as the last day of the month unless the end
 date of subsequent anti-cancer therapy is before that date. In that case, the incomplete
 anti-cancer therapy start date will be imputed as the end date of the anti-cancer therapy.
- If both day and month are missing, no imputation will be performed.
- Incomplete subsequent anti-cancer therapy stop dates will not be imputed.

9.12 Analysis software

All analyses will be performed using SAS® Software version 9.4 or higher.

10 Study Participants

The subsections in this section include specifications for reporting participant disposition and study treatment/study discontinuations. Additionally, procedures for reporting protocol deviations are provided.

10.1 Disposition of Participants and Discontinuations

The number and percentage of participants in each of the below disposition categories will be presented by analysis group and total, where applicable. Percentages will be presented with respect to the number of treated participants

- Total number of participants screened (i.e. participants who gave informed consent)
- Number of participants who discontinued from the study prior to treatment overall and grouped by the main reason (e.g. failure to meet inclusion or exclusion criteria, withdrawal of consent)
- Number and percentage of treated participants.
- Number and percentage of treated participants who discontinued the study treatment (overall and by primary reason)
- · The end of study status will be summarized by:
 - Number and percentage of participants who completed or prematurely discontinued the study, grouped by main reason

Additionally, the number of participants screened, and enrolled in each analysis population will be provided overall, by region, by country within region, and by site.

A listing of pertinent participant disposition information for each participant will be provided.

10.2 Protocol Deviations

Analysis Set: FAS/SAF

Important protocol deviations (IPDs) are protocol deviations that might significantly affect the completeness, accuracy, and/or reliability of the study data or that might significantly affect a participant's rights, safety, or well-being.

Important protocol deviations include:

- Participants enrolled and dosed on the study who did not satisfy enrolment criteria
- Participants that develop withdrawal criteria whilst on the study but are not withdrawn
- Participants that receive an excluded concomitant medication
- Failure to collect data necessary to interpret primary endpoints
- Failure to collect necessary key safety data
- Deviation from Good Clinical Practice (GCP)
- Any other protocol deviation that might significantly affect the completeness, accuracy, and/or reliability of the study data or that might significantly affect a participant's rights, safety, or well-being.

IPDs will be identified for all participants by either site monitoring, medical review processes or programming and confirmed prior to or at the Data Review Meeting, at the latest.

All protocol deviations will be documented in the Clinical Trial Management System (CTMS).

All IPDs will be included in SDTM datasets whether identified through site monitoring, medical review or programming.

A listing will be provided for all protocol deviations and the subset of protocol deviations that were attributed to the impact of the COVID-19 pandemic will be identified in this listing.

11 Demographics and Other Baseline Characteristics

11.1 Demographics

Analysis Set: FAS/SAF

Demographic characteristics and physical measurements will be summarized descriptively using the following information from the Demography eCRF page and the baseline vital signs assessment:

- Sex: Male, Female
- Race: White, Black or African American, Asian, American Indian or Alaska Native, Native Hawaiian or Other Pacific Islander, Other, Not Collected at this Site
- Ethnic origin: Hispanic or Latino/Not Hispanic or Latino
- Ethnic origin: Japanese or Not Japanese
- Age (years)
- Age categories:
 - < 65 years,

 - ≥ 65 years
 - 0 65-74
 - 0 75-84
 - o ≥85 years
- Pooled Region:
 - North America
 - Europe
- BSA (m²) at Baseline
- Weight (kg)
- BMI (kg/m²) at Baseline
- Eastern Cooperative Oncology Group (ECOG) Performance status (0,1,2,3,4)

Specifications for computation:

- Age [years]
 - (date of given informed consent date of birth + 1) / 365.25
 - In case of missing day for at least one date, but month and year available for both dates:
 - For the derivation of age, the day of informed consent and the day of birth will be set to 1 and the formula above will be used
 - In case of missing month for at least one date, but year available for both dates:

For the derivation of age, the day and the month of informed consent and the day and month of birth will be set to 1 and the formula above will be used

The integer part of the calculated age, without rounding, will be used for reporting purposes.

• BSA
$$[m^2] = \sqrt{\frac{\text{height[cm]} \times \text{weight[kg]}}{3600}}$$

- BMI [kg/m²] = $\frac{\text{weight [kg]}}{\text{height[cm]}^2} \times 10000$
- Site codes will be used for the determination of the participant's geographic region.

11.2 Medical History

Analysis Set: FAS/SAF

Participant medical history will be summarized from the "Medical History" eCRF page, using the most recent MedDRA version available. A listing of medical history data by participant will include all the relevant data fields as collected on the "Medical History" CRF page.

11.3 Other Baseline Characteristics

Analysis Set: FAS/SAF

11.3.1 Disease History

The following information on disease characteristics collected at baseline will be listed:

- Site of primary tumor
- Tumor mutation, i.e. ARID1A, ATX, DRXX, and/or ATM
- Time since initial cancer diagnosis
- Time since date of documented, locally advanced, inoperable or metastatic disease diagnosis
- TNM staging at initial diagnosis

- TNM staging at study entry
- ECOG performance status at baseline

11.3.2 Prior Anti-Cancer Therapy

The prior anti-cancer therapies are collected under the "Prior Anti-Cancer Therapy", "Prior Anti-Cancer Radiotherapy" and "Prior Anti-Cancer Surgery" eCRF pages.

The listings of prior anti-cancer treatments and procedures will be provided as follows. These will include the participant identification number, and all the relevant collected data-fields on the corresponding eCRF pages.

- Listing of prior anti-cancer drug therapies
- Listing of prior anti-cancer radiotherapy
- Listing of prior anti-cancer surgeries.

12 Previous or Concomitant Medications/Procedures

Analysis Set: FAS/SAF

Concomitant medications are medications, other than study treatment, which are taken by participants any time during the On-treatment Period.

Previous medications are medications, other than study treatment and pre-medications for study treatments, which started before the first administration of study treatment.

A medication may be classified as both concomitant and previous. The respective flags will be derived based on start and end date. Please refer to Section 9.12.3 for details on the classification of medications with partial start and end dates.

Concomitant and previous medication details captured on the "Prior and Concomitant Medications" eCRF page will be included in a listing, along with a flag to indicate whether the medication was identified as a previous or concomitant medication.

All relevant details of Concurrent procedures captured on the CRF page "Non-pharmacological Treatments or Procedures" will be listed.

13 Study Treatment: Compliance and Exposure

Analysis Set: FAS/SAF

All dosing calculations and summaries will be based on "M4344 Administration Details" CRF page. During each 21-day cycle, M4344 is taken once a day, every day of the treatment cycle.

Total number of administrations of M4344

Total number of administrations is calculated as the sum of administrations that a subject received across cycles where actual dose received is > 0 mg.

Total cumulative dose

Total cumulative dose for the study treatment is the sum of the actual dose amounts that a subject receives across all cycles.

Duration of exposure

Duration of exposure (weeks) =
$$\left(\frac{\text{date of last dose-date of first dose+1}}{7}\right)$$

Total planned dose

Total planned dose (mg) is calculated based on the established Part C planned dose as follows:

Planned cumulative dose (mg) = Cohort dose (mg/administration) × duration of exposure (days)

Dose intensity

Relative dose intensity

The relative dose intensity (%) is calculated by dividing the dose intensity by the planned daily dose of the study drug.

The following will be summarized:

- Duration of therapy (weeks): by summary statistics and counts/percentages of the following categories: ≤ 3 weeks, > 3 - 6 weeks, > 6 - 9 weeks, > 9 - 12 weeks, > 12 weeks
- Total number of administrations
- Total cumulative doses (mg)
- Dose intensity (mg/day)
- Relative dose intensity (%): by summary statistics and counts/percentages of the following categories: < 60%, ≥ 60% - < 80%, ≥ 80% - < 90%, ≥ 90% - ≤110%, >110%
- Minimum dose compliance (%): < 50%; ≥ 50% < 70%; ≥ 70% < 90%; ≥ 90% relative to initially planned dose

14 Efficacy Analyses

Analysis Set: FAS/SAF

